## **1 SPECIFIC AIMS**

Pain in both youth and adults is a complex, subjective and personal experience, and remains poorly understood. One particularly perplexing dimension of some forms of pain is the tendency of pain to spread outside of an affected body site to adjacent location, and then to unaffected body sites. Such widespread pain may reflect an altered spatial tuning of somatosensory processing, such that lateral inhibition is diminished, thereby allowing pain to spread. To date, no therapies exist which are designed specifically to diminish or even reverse the spatial spread of pain. However, training in two-point discrimination holds the potential to retune spatial aspects of somatosensory processing and may represent a novel therapy for widespread pain. Thus, the present investigation will test the following aims:

**Aim 1. Do youth with chronic pain have disrupted spatial tuning of somatosensory processing?** Deficits in two point tactile discrimination have long been noted in adults with chronic pain, but such deficits remain poorly documented in pediatric chronic pain patients. In order to determine if such deficits exist, youth with both chronic pain and healthy youth will undergo assessment of two point discrimination thresholds.

**Aim 2. Does two-point discrimination training result in diminished pain and disability in youth with somatic pain?** After initial characterization of tactile discrimination thresholds, youth with chronic pain will participate in multiple sessions of either two-point discrimination training or a single-point spatially-directed attentional control condition. Training will involve up to 9 additional sessions. Efficacy of training will be assessed by 1) reductions in the spatial extent of pain, 2) reductions in pain intensity and unpleasantness, and 3) reductions in pain-related disability.

## **2 SIGNIFICANCE AND INNOVATION**

### **2.1 Scientific Premise**

Highly disabling persistent pain is a frequent complaint in children, with prevalence estimated at approximately five percent in Western societies (Huguet and Miro, 2008; Hechler et al., 2014). Pain prevalence rates increase with age (King et al., 2011) and as such, chronic pain in adolescence represents a significant economic problem in the USA (Groenewald et al., 2014). Adolescence is a critical period for development physically, psychologically and socially, and pain severely interferes with such an important phase of life (O'Sullivan et al., 2012). Adequate management of pain in adolescents should clearly be a goal in itself, but the evidence suggests that management of pain in young people may also help prevent pain in adults (Hestbaek et al., 2006).

From a mechanistic standpoint, fundamental questions about pain remain unanswered, and this has meant the treatment needs of pain sufferers have largely been unmet. To date the intensity of pain has been a focus of investigation and

treatment, but pain intensity is only one dimension of the pain experience. Research into the spatial dimension of pain has been grossly neglected in comparison; we still do not fully understand how the nervous system processes and spatially tunes incoming sensory information from the body. This avenue of inquiry is critical, given that one of the most common and intriguing symptoms of chronic pain is the spread of pain well beyond the site of the original injury. Our knowledge of sensory function in adolescents is particularly lacking.

Several lines of evidence point towards abnormal processing of sensory information in adult patients with chronic pain disorders. For example, when it comes to a painful body part, sufferers are typically unable to perceive the sensation of two individual stimuli on the skin when those two points are located close together in space (termed two-point discrimination) (Flor et al., 2001; Lotze and Moseley, 2007; Wand et al., 2010). This poor tactile acuity indicates abnormality in the nervous system's normal spatial tuning, or surround inhibition, of sensory information; in patients it appears that each sensory stimulus is not activating a distinct population of neurons as it would in a healthy pain-free person (Defrin et al., 2008), (Gardner et al., 2000). Poor tactile acuity has been correlated with pain intensity (Flor et al., 2006; Lotze and Moseley, 2007) and with the spread of pain (Maihofner et al., 2003, 2004). Not only do patients with CRPS have impaired 2-point discrimination in their affected extremities compared with their unaffected extremities, but they also have diminished ability to learn 2-point discrimination in comparison with control subjects (Maihofner et al., 2007). All this suggests a global impairment in spatial tuning within and in comparison to external controls.

An important randomized trial in adults with phantom limb pain trained patients' tactile acuity with repeated stimulation over the stump. The training led to improved pain levels, together with increased tactile acuity and reversal of the associated abnormal brain activation patterns (Flor et al., 2001). Regarding chronic limb pain, Moseley and colleagues found that repetitive stimulation of the skin improved pain levels and patients' tactile acuity in the affected area (Moseley et al., 2008). Importantly, the stimulation program involved instructions on attending to and evaluating the nature of the stimulation – that is, a discrimination task. Tactile stimulation alone did not have the same effects.

Our translational work with spatial aspects of pain provides a mechanistic rationale for extending and refining the work of Moseley. First, using lasers to deliver noxious heat in two different patterns - two simultaneous points (4-8 cm separation distance, 5 mm diameter) or a contiguous line (4-8 cm long, 5 mm width), we sought to identify a psychophysical correlate of lateral inhibition (Quevedo et al., 2017). Despite the considerably larger surface area being stimulated with the line, participants perceived the two point stimuli as more intense. This suggests that, in healthy individuals, there is a lateral inhibition that was recruited by the line stimuli, but not by the two point stimuli (Quevedo et al., 2017).

This lateral inhibition may be modified by attention. Using contact heat stimuli, we routinely demonstrate spatial summation of pain (i.e., enhanced pain response) when two stimuli are delivered at 10 cm separation distances. This occurs when

participants are instructed to make one overall rating of pain. However, when subjects are given a different attentional directive - i.e. to rate pain from each probe separately - spatial summation of pain is abolished and some inhibition is generated (Quevedo and Coghill, 2007). We have hypothesized that to accomplish this task, lateral inhibition at some level of the neuraxis is increased by the attentional directive. This, in turn, minimizes spatial interactions among populations of neurons responding to each stimulus, and abolishes spatial summation. Moreover, this increased lateral inhibition may sufficiently reduce the total population response to account for inhibition unmasked at distal stimulation sites (Quevedo and Coghill, 2007).

Despite this growing body of research in adults, demonstration of these processes in children and adolescents is lagging behind. What if we were able to demonstrate deficits in and restore spatial tuning of the sensory nervous system in adolescents with widespread pain? This project aims to meet this objective, using a targeted and innovative treatment paradigm.

## **2.2 Innovation and Importance of this Study**

To date, there are no therapies targeted specifically at minimizing and reducing the spatial spread of pain. As such, if this study is successful, an important new therapy for pain may emerge.

## **2.3 Supporting Data-Previous Evidence**

The proposed investigation is highly novel and builds on our prior spatial studies described above. To date, no investigations have used two point discrimination training to demonstrate deficits in children and adolescents with chronic pain as have been found in adults or as a potential treatment for widespread pain.

## **3 STUDY DESIGN**

Prior to commencing this investigation we will optimize the tactile discrimination threshold testing (i.e. as per baseline visit, below), and the training conditions, in up to ten participants (patients and/or healthy controls). This will serve as a pilot to refine operational aspects of study procedures before we commence the main investigation proposed herein. Following this, youth with either chronic pain (ages 10-17, n=40) or healthy youth (ages 10-17, n=20) will undergo assessments of two-point and single-point discrimination thresholds in an initial session (Aim 1). After this initial session, youth with chronic pain will participate in up to 9 additional sessions of attentional training (Aim 2). These chronic pain patients will be randomized to either two-point discrimination training (n=20) or a single-point spatially-directed attentional control condition (n=20). Participants will not be informed of which intervention they will receive (single-blind study). Psychological questionnaires will be completed in the first and last sessions in order to determine how these variables relate to tactile discrimination and response to training.

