## 4 SELECTION AND ENROLLMENT OF PARTICIPANTS

### 4.1 Inclusion Criteria

#### Chronic Pain Patients:

Somatically located chronic pain including amplified musculoskeletal pain syndrome, complex regional pain syndrome, low back pain, fibromyalgia, other forms of chronic, widespread pain.

Male or female, 10-17 years (inclusive)

High fluency in written and oral English language

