**9. STATISTICS**

**9.1 Statistical Analysis Plan**

**Aim 1:**

A mixed model analysis of variance will be utilized to determine differences between groups (chronic pain patients vs. healthy controls - between factor) and body site (within factor), and group X body site interactions.

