## **9.2 Number of Participants to be Enrolled**

This is the first investigation of an entirely novel question, and will be used to determine both effect size and variability. Thus, we will apply a heuristic approach based on prior experience obtained within-subjects variability in pain ratings in studies of spatial aspects in acute experimental pain in healthy adults (Quevedo and Coghill, 2007; Quevedo et al., 2017). With these studies, we have obtained reproducible results from 15 subjects in within subjects designs. Thus, we have selected N=20 per group to compensate for the reduced power of the between subjects design. Up to 10 additional participants will serve to optimize operational aspects of study procedures as potential pilot subjects.

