## **9.3 Level of Significance**

Statistical significance will be defined by  $p<0.05$ .

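### Aim 1 compares 40 patients of mixed diagnosis with 20 controls by an ANOVA that by default assumes one variance; stating separate variances would keep the test calibrated at little cost

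*Protocol*

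**What the plan says.** Section 3 sets the Aim 1 groups: "youth with either chronic pain (ages 10-17, n=40) or healthy youth (ages 10-17, n=20"). Section 9.1, under Aim 1, names the method: "A mixed model analysis of variance will be utilized to determine differences between groups (chronic pain patients vs. healthy controls - between factor"), with body site as the within factor and a group by site interaction. It does not say whether the two groups share a variance.

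The patient group is broad. Section 4.1 admits "Somatically located chronic pain including amplified musculoskeletal pain syndrome, complex regional pain syndrome, low back pain, fibromyalgia, other forms of chronic, widespread pain". Controls need only be in good general health.

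Section 9.3 sets the threshold: "Statistical significance will be defined by" p<0.05, with no mention of one or two sides. Section 9.2 gives no SD, effect size or power target. It describes the study's purpose: "This is the first investigation of an entirely novel question, and will be used to determine both effect size and variability".

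**The concern.** The ordinary between/within ANOVA estimates one error variance from both groups together. When group sizes are equal this does little harm even if the variances differ. At 40 v 20 the pooled variance is weighted towards the larger group, while the true uncertainty of the difference is driven mainly by the smaller one. If the patients are more variable, the standard error of the group difference is too large and the test is conservative. If the controls are more variable, it is too small and the test rejects too often.

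Equal variance should not be taken for granted here. A group that pools several pain diagnoses may contain youth with a marked deficit, a slight one or none, and so may spread more widely than healthy controls. What is at stake is the calibration of the Aim 1 test and interval and, in the more plausible direction, some of the power to find the deficit that Aim 1 looks for.

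**Working it through.** **Inputs.** From the protocol: 40 patients and 20 controls (section 3), and p<0.05 (section 9.3), taken as two-sided. Assumed, because the protocol gives none: the SD ratio between the groups, the share *f* of patients with a deficit, and its size *d* in control SDs.

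**The plan's own figure.** The choice of 20 per group (section 9.2) is a heuristic with no SD, effect or power behind it, so it cannot be reproduced. For scale, with equal variances 40 v 20 gives about 80% power at 2.80 × √(1/40 + 1/20) = 2.80 × 0.274 = 0.77 SD.

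**Standard error of the group difference.** With variances v1 (patients) and v2 (controls):

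- pooled SE² = [(39·v1 + 19·v2)/58] × (1/40 + 1/20)
- true SE² = v1/40 + v2/20

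Patient SD 1.5, control SD 1:

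- pooled: (87.75 + 19)/58 × 0.075 = 0.1380, SE 0.372
- true: 0.05625 + 0.05 = 0.10625, SE 0.326
- ratio 1.14, so the pooled SE is 14% too large

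Control SD 1.5, patient SD 1:

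- pooled: (39 + 42.75)/58 × 0.075 = 0.1057, SE 0.325
- true: 0.025 + 0.1125 = 0.1375, SE 0.371
- ratio 0.88, so the pooled SE is 12% too small

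At 30 v 30 the two formulas coincide, since both equal (v1 + v2)/30. The exposure therefore comes from the 2:1 sizes.

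**Actual error of a nominal 5% test.** Simulation with normal data and one threshold per participant, pooled t-test against the Welch test. Repeated runs of the pooled test give 2.6 to 2.7% when the patient SD is 1.5 times the control SD, and 8.5 to 8.7% in the reverse case. The Welch test stays at about 5% in both.

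**Power when only some patients have a deficit.** The patient variance is then 1 + f(1−f)d² times the control variance.

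| Share affected | Deficit (control SDs) | Pooled power | Separate-variance power |
|---|---|---|---|
| 1/4 | 1 | 12.7% | 13.9% |
| 1/4 | 2 | 28.7% | 35.6% |
| 1/4 | 3 | 43.6% | 57.4% |
| 1/3 | 1.5 | 33% | 38% |
| 1/3 | 2 | 47% | 55% |
| 1/3 | 3 | 68% | 80% |
| 1/2 | 1 | 37.7% | 40.1% |
| 1/2 | 1.5 | 63.8% | 69.0% |
| 1/2 | 2 | 82.0% | 87.4% |
| 3/4 | 1 | 72.4% | 73.7% |
| All | 0.8 | 82.0% | 81.2% |
| All | 1 | 94.9% | 94.5% |

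**How large a deficit the 1.5 ratio implies.** If partial deficit is the only source of extra spread, an SD ratio of 1.5 needs f(1−f)d² = 1.25. At f = 0.5, which needs the smallest deficit, d = √(1.25/0.25) = 2.2 control SDs.

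**Dilution.** At d = 1, pooled power falls from 94.9% with all patients affected to 37.7% with half affected, a drop of 57 points. Separate variances recover about 2.5 of them.

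**The case against.** The strongest objection is that nothing in section 9.1 is wrong as written. It names a mixed model and is silent on the variance structure. Such a model can carry group-specific variances, and that detail is often left to a statistical analysis plan, which is not at hand here. This stands in part. A reader might infer that the protocol prescribes pooling, but it does not; pooling is only the default reading of the method it names.

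A second tempting inference is that the protocol itself shows the deficit to be confined to some patients or sites. Section 2.1 says that "patients with CRPS have impaired 2-point discrimination in their affected extremities compared with their unaffected extremities". That is a relative statement about one diagnosis; it does not say that unaffected sites are normal. The same paragraph goes on to suggest a general impairment, also against outside controls. Moreover, a difference between sites within a patient is what the body-site factor and its interaction address; it is not evidence of greater spread between patients. The reason to doubt equal variances therefore rests on the mix of diagnoses in section 4.1, which makes unequal spread plausible but does not establish it.

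Third, the consequences are modest. In the more plausible direction the test errs on the safe side, so a positive Aim 1 result is not undermined. The documents offer no particular reason to expect controls to be the more variable group. No power target exists to be missed. The simulation also simplifies the plan to one threshold per participant and does not cover the interaction test. All of this stands. It lowers the severity but does not remove the case for an inexpensive safeguard.

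**Conclusion.** The point holds as a low-severity improvement, not as an error in the protocol. With 40 v 20 and the default single variance, the Aim 1 group test does not keep its nominal 5% if the variances differ: about 2.7% or 8.7% at an assumed SD ratio of 1.5, depending on which group is the more variable. The loss of power under partial deficits depends wholly on the assumed share and size. It is about 1 to 5 points for modest deficits, 7 to 14 points only where a third or fewer of patients have a deficit of 2 SD or more, and none if every patient is equally affected.

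It would go too far to say that pooling explains most of the power lost when only some patients are affected. Most of that loss comes from the diluted mean difference, which no choice of variance model restores. Nor are all error bars too wide when patients are the more variable group: pooling widens the interval for the group difference and for the controls, but makes the patients' own interval too narrow.

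**What to change.** In section 9.1, Aim 1, add that patients and controls are given separate variances, in one of two ways:

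- a mixed model with group-specific between-person and residual variances and Satterthwaite-type degrees of freedom; or
- Welch tests, on each participant's mean threshold for the group effect and on within-participant site differences for the group by site interaction.

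Report the group difference with its 95% CI from that analysis, and each group's SD. Reporting the two SDs also serves the purpose in section 9.2 of learning about variability, which a single pooled SD would obscure.

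The cost is a sentence or two of analysis wording and no new data. If the variances are in fact equal, the price is under 1 point of power (for example 82.0% v 81.2% at a 0.8 SD difference). If a statistical analysis plan already specifies separate variances, a cross-reference to it is enough.

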## 4 SELECTION AND ENROLLMENT OF PARTICIPANTS

### 4.1 Inclusion Criteria

#### Chronic Pain Patients:

Somatically located chronic pain including amplified musculoskeletal pain syndrome, complex regional pain syndrome, low back pain, fibromyalgia, other forms of chronic, widespread pain.

Male or female, 10-17 years (inclusive)

High fluency in written and oral English language

#### Control Participants:

Youth in good general health

Male or female, 10-17 years (inclusive)

High fluency in written and oral English language

### 4.2 Exclusion Criteria

Present significant mental health disorder as defined by DSM V (e.g. psychosis, bipolar disorder, major depression), alcohol or drug dependence, or documented developmental delays or impairments (e.g., autism, cerebral palsy, or mental retardation) of a magnitude that would interfere with adherence to study requirements or safe participation in the study

Primary complaint of migraine or visceral (abdominal) pain, with minimal somatic pain.

### 4.3 Participant Withdrawal Criteria

Participant (or legal guardian) declines further study participation.

Participant fails to comply with experimental protocol or instructions of study staff.

Identification of brain, neurologic, or severe psychiatric abnormalities that may confound procedures.

In the investigator's judgment, it is in the participant's best interest.

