### **6.5 Psychological Assessment/Questionnaires**

Variation in psychological states can contribute substantially to the construction of the experience of pain, and may importantly influence attentional processes related to pain. Thus, participants will undergo extensive psychological characterization with a particular focus on variables known to influence pain. Many scales will be useful for enabling comparisons of these patients with chronic pain patients in other studies, and are part of our standard testing battery.

Anxiety: The PROMIS Anxiety pediatric scales will be used to assess anxiety. The SCARED anxiety scale will be used to further characterize anxiety.

Mood and Affect: The PROMIS Depression pediatric scales will be used to assess depression. The Positive and Negative Affect Schedule - Expanded will be used to characterize mood and affect.

Mindfulness: The Freiburg Mindfulness Inventory will be used to assess mindfulness.

Impulsivity: The Barratt Impulsiveness Scale will be used to assess impulsivity.

Handedness: The Edinburgh Handedness Inventory will be used to assess the degree of handedness and will be critical in the interpretation of differences in the lateralization of nociceptive processing.

Sleep: Sleep deprivation may substantially alter pain sensitivity. The Epworth Sleepiness Scale will be used to quantify the level of daytime sleepiness, while the Pittsburgh Sleep Quality Index will be used to assess sleep quality.

Pain Interference, Disability, and Catastrophizing: The PROMIS Pain Interference Scale (pediatric version) will be used to assess how much pain interferes with daily living. Pediatric versions of the pain catastrophizing scale will be used to assess pain-related catastrophizing, while the Functional Disability Index will be used to characterize disability.

Social Status and Discrimination: Insurance, income, education level, and experience of discrimination will be used to quantify socio-economic variables.

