## 7 Study Visits

The duration of two-point discrimination needed to improve pain remains completely unknown. To optimize retention, we may truncate the number of visits, depending on subject availability, with procedures in Visit 10 being performed at the final visit. Healthy control participants will only participate in the baseline visit.

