### 7.1 Baseline + Intervention - Visit 1 (up to 3 hours)

- Completion of informed consent/assent prior to initiation of study procedures
- Obtain information for payment, provide ClinCard
- Randomize to intervention
- Review medical history
- Document all concomitant medications including prescribed, over the counter, and nutraceutical supplements
- Administer questionnaires
- Assess pain intensity, unpleasantness, qualitative aspects of pain
- Assess spatial extent of pain (body map or patient's own photo)
- Demonstration of two-point/single-point discrimination procedure
- Assess two-point/single-point discrimination
- Initiate intervention (TPD training or Control)
- Assess pain intensity, unpleasantness
- Assess spatial extent of pain

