### 7.2 Intervention - Visits 2-9 (1 hour)

- Determine any changes in medications or concurrent conditions
- Assess pain intensity, unpleasantness, qualitative aspects of pain

Assess spatial extent of pain  
Continue intervention (TPD training or Control)  
Assess pain intensity, unpleasantness, qualitative aspects of pain  
Assess spatial extent of pain

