**7.3. Intervention+Completion - Visit 10 (up to 3 hours)**

Assess pain intensity, unpleasantness, qualitative aspects of pain  
Assess spatial extent of pain  
Final intervention (TPD training or Control)  
Assess two-point/single-point discrimination  
Assess pain intensity, unpleasantness, qualitative aspects of pain  
Assess spatial extent of pain  
Administer psychological questionnaires

Note that some of the procedures above may be omitted for the purpose of streamlining the study visits, or if procedures are deemed to be incongruent with the participants' ongoing clinical treatments. Omitting these procedures would reduce participant burden and would have no impact on safety.

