**Aim 2:**

To maximize the utility of data collected, a mixed model analysis of variance will be utilized to determine differences between groups (between factor), differences over time (within factor), and time X group interactions.

Outcome variables of interest include 1) reductions in area of pain, 2) reductions in pain intensity and unpleasantness, 3) reductions in pain-related disability

Control variables include: 1) Improvements in tactile discrimination thresholds, 2) data from psychological questionnaires. These variables may be added as covariates to the overall model, or may be used to perform a manipulation check. JMP or R software will be used to perform analyses

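### Section 9.4 drops randomised patients with fewer than 5 sessions along with data already collected, and a patient who stops between visits without notice has no post-baseline disability value

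*Protocol*

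**What the plan says.** **Analysis set.** Protocol section 9.4 treats completion of fewer than 5 sessions as excessive missing data and includes everyone else. Healthy controls attend only the baseline visit, so the rule is read here as applying to the randomised patients in Aim 2.

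**Withdrawal.** Section 4.3 is a single list of four grounds: the participant or guardian declines to go on with the study, "Participant fails to comply with experimental protocol or instructions of study staff", a neurological or severe psychiatric finding, and the investigator's judgment of the participant's interest. It does not distinguish stopping training from ending assessment, and it describes no assessment at or after withdrawal.

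**Disability.** The Aim 2 outcomes in section 9.1 include "3) reductions in pain-related disability". Section 6.5 places the instrument in the questionnaire battery, "while the Functional Disability Index will be used to characterize disability", and PROMIS Pain Interference sits in the same battery.

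**Timing.** Section 3 states: "Psychological questionnaires will be completed in the first and last sessions". Section 7.1 (Visit 1) lists "Administer questionnaires" and section 7.3 (Visit 10) lists "Administer psychological questionnaires". Section 7.2, which covers Visits 2-9, lists no questionnaire. Pain ratings and the spatial extent of pain are listed twice at every visit.

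**Truncation.** Section 7 allows early completion: "we may truncate the number of visits, depending on subject availability, with procedures in Visit 10 being performed at the final visit".

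**The concern.** The number of sessions completed is determined after randomisation and may depend on the assigned training and on how the patient is doing. An analysis set defined by it no longer compares the groups as randomised. It also sits badly with section 9.1, which gives making the most of the collected data as the reason for using a mixed model.

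The second gap is in collection. Disability has one scheduled post-baseline measurement, and it depends on staff knowing that a visit is the last. Someone whose last attended visit was run as an ordinary Visit 2-9 has none. Non-compliance with training is not a refusal to answer a short questionnaire, but section 4.3 treats both as withdrawal. A later analysis plan can restore data that are on file; it cannot restore a disability value that was never collected. With 20 patients per arm, each patient lost is 1/20 = 5% of an arm.

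**Working it through.** No figure in the protocol is disputed. The N = 20 per group in section 9.2 is heuristic, with no effect size, SD, power or dropout rate, so there is no calculation to reproduce.

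**1. What is on file after an unannounced stop.** Sections 7.1 and 7.2 list pain ratings and a body map twice per visit. After session k (k = 1 to 9) there are up to 2k pain assessments, up to 2k body maps and 1 disability value (baseline). The counts are upper limits because section 7.3 allows procedures to be omitted.

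| Stops after session | Pain assessments | Body maps | Disability values | In the 9.4 set? |
|---|---|---|---|---|
| 4 | 8 | 8 | 1 | no |
| 5 | 10 | 10 | 1 | yes |
| 9 | 18 | 18 | 1 | yes |

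So two groups are affected differently.
- Stops after sessions 1-4: section 9.4 removes everything, including pain data already collected.
- Unannounced stops after sessions 5-9: the patient stays in the set but has no disability change to contribute. Collecting disability late helps only this group unless section 9.4 also changes.

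Section 7 also sets no minimum number of visits. A patient truncated to 4 visits could have a complete final assessment and still be excluded by section 9.4.

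**2. Precision for disability.** Assumptions: two-sample t test on change, two-sided 5% (section 9.3 gives p < 0.05 without sidedness), 80% power as a reference only, noncentral t. Losses of 0, 1 or 2 of 20 per arm are assumed.

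| Lost per arm | n per arm | Detectable difference, 80% power | Power at 0.909 SD |
|---|---|---|---|
| 0 | 20 | 0.909 SD | 80.0% |
| 1 | 19 | 0.934 SD | 77.8% |
| 2 | 18 | 0.961 SD | 75.5% |

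If 2 per arm are lost and both are recovered, the gain is 0.961 − 0.909 = 0.052 SD, or 80.0 − 75.5 = 4.5 points of power. Recovering one of the two gains 0.961 − 0.934 = 0.027 SD.

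**3. Possible bias from unequal loss.** Let r be the assumed correlation between the tendency to leave and poor change, and p1 and p2 the proportions lost. Then bias = r × [φ(z_p1)/(1 − p1) − φ(z_p2)/(1 − p2)], and SE = √(1/n1 + 1/n2) in SD units. The bracketed terms are 0.1086 at 5% loss, 0.1950 at 10% and 0.2743 at 15%.

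| Lost (of 20) | r | Bias | SE | Two-sided error (normal) |
|---|---|---|---|---|
| 2 vs 1 | 0.3 | 0.3 × 0.0864 = 0.026 SD | 0.329 | 5.07% |
| 2 vs 1 | 0.5 | 0.5 × 0.0864 = 0.043 SD | 0.329 | 5.20% |
| 3 vs 1 | 0.3 | 0.3 × 0.1657 = 0.050 SD | 0.334 | 5.25% |
| 3 vs 1 | 0.5 | 0.5 × 0.1657 = 0.083 SD | 0.334 | 5.71% |

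Equal loss, related to outcome equally in both arms, gives zero bias. The same formula gives the scale for patients removed by section 9.4, if the assumed losses are read as exclusions.

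**The case against.** The strongest reply is that nothing here is inconsistent. First-and-last timing of the questionnaires agrees across sections 3, 7, 7.1 and 7.3, and limiting a long battery to two sessions is a reasonable choice about burden for 10-17 year olds. That stands, and the timing itself is not criticised.

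A reader might infer that every early stop loses the disability outcome. The text does not support that: section 7 moves the Visit 10 procedures to the final visit when visits are truncated for availability, and a stop decided at a visit could be handled the same way. Only unannounced stops remain. Widening the section 7 wording would not reach them, because staff cannot know at the time that the visit is the last.

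A reader might also infer that section 4.3 forbids later contact, or that the pain outcomes share the collection gap. Section 4.3 is silent rather than prohibitive, and pain and body maps are scheduled at every visit. Families who decline further participation, or who cannot be reached, will yield nothing, so the recoverable group is a fraction of a small one.

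The numerical effect is small and every loss rate is assumed; this too stands. Section 9.2 claims no power, so 80% is only a yardstick. Finally, data excluded by section 9.4 are on file and a statistical analysis plan could define a fuller set. That is true, but the protocol does not leave the set open. It fixes a rule, and it is the stated rule that should change.

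**Conclusion.** The point holds as a minor, low-cost improvement in two parts. The section 9.4 rule comes first: it conditions on a post-randomisation event and discards up to 8 pain assessments and 8 body maps for a patient who stops after session 4. The missing disability value after an unannounced stop comes second. By itself it affects the current analysis set only for stops after sessions 5-9.

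The gain from collecting disability after such a stop is at most about 0.05 SD in detectable difference, assuming 2 of 20 lost per arm and all recovered. Bias under the assumed imbalances is 0.03 to 0.08 SD against a standard error of 0.33 SD. The protocol gives no withdrawal rate, so these are illustrations, not predictions. A claim that the trial's conclusions are seriously threatened, or that a stated figure is wrong, would go beyond the document.

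**What to change.** 1. **Section 9.4.** Make the main Aim 2 analysis include all randomised patients with outcome data, by assigned arm. Keep the set with 5 or more sessions as a supportive analysis.
2. **Section 4.3.** State that stopping training does not by itself end data collection. Unless the family declines, or the investigator judges contact not to be in the child's interest, seek the Functional Disability Index and PROMIS Pain Interference once, at the stopping visit or by one remote contact. Record the date and the reason for stopping. The investigator exception matters because section 11.1 notes that the questionnaires may cause discomfort. The grounds for stopping training stay as they are.

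The cost is one or two sentences in each section and a short contact for the few who stop without notice, with no new instrument and no extra patients. The downside is that some disability values will be off schedule and partly remote, which is why the date must be recorded.
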